1.2.2. Subject Populations for Analysis

The following analysis populations will be defined for this study:

Intent-to-Treat: will include any subject randomized into the study that receives a dose of study drug and that has completed at least one post-baseline efficacy measurement while on study medication;

Safety: Any subject randomized into the study that receives a dose of study drug;

Per-Protocol: Any subject who is randomized and receives the protocol required study drug exposure and required protocol processing.

Efficacy analyses will be performed on the Intent-to-Treat population and the Per-Protocol population. Safety summaries will be based on Safety set. Subject characteristics will be presented for all subjects randomized.

1.2.3. Subject Disposition

Study completion and reasons for discontinuation for all randomized subjects in the double-blind phase will be summarized for each treatment group. Discontinuations by reason will be tabulated by visit for each treatment group.

Time to discontinuation due to adverse events, lack of efficacy and for any reason will be analyzed using Kaplan-Meier survival techniques; the log-rank test will be used for group comparison.

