#### **Number of subjects (planned):**

Approximately 164 subjects randomized (82 per arm, 1:1 randomization scheme)

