## **Overall Design:**

This is a multicenter, randomized, double-blind, placebo-controlled study to be conducted in the United States. Approximately 164 subjects with treatment-resistant pruritus diagnosed with atopic dermatitis, who satisfy the selection criteria for the study, will be randomized to receive either tradipitant 85 mg or matching placebo BID.

The study is divided into two phases: the pre-treatment phase and the evaluation phase. The pre-treatment phase includes a screening and a baseline visit where subjects' eligibility for the study will be assessed. Washout of medications per Section 7.2 will occur during the screening phase. The evaluation phase includes 8 weeks of randomized double-blind treatment. In clinic evaluations will occur at Screening, Baseline, and Weeks 2, 4, 6, and 8.

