1. STATISTICS

1.1. Sample Size and Accrual

The sample size chosen for this study is not based on statistical considerations. This sample size was chosen after taking into consideration historical data Approximately 164 patients will be randomized.

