1.2.1. General

Statistical analyses will be performed using two-sided tests.

Data will be summarized by treatment group (and by visit when applicable), with respect to demographic and baseline characteristics, efficacy variables, and safety variables.

Summary statistics will include the mean, N, standard deviation, median, minimum, and maximum values for continuous variables, and frequencies and percentages for categorical variables.

For the analyses of change from baseline, only subjects with a baseline and at least one (1) post-baseline measure will be included in the analysis. Unless otherwise specified, baseline is defined as the latest non-missing observation across all the visits in the screening phase, before the active study drug begins. Endpoint will be the latest non-missing observation across all the post-baseline visits in the evaluation phase.

Low enrolling sites will be pooled for analysis and the pooling algorithm will be determined prior to breaking the blind. The goal of pooling low enrolling sites is to have a sufficient number of subjects per treatment group within a site for the analysis models and for the evaluation of the treatment-by-site interaction for the primary endpoint. Unless otherwise specified, the pooled sites will only be used in the analyses where site has an effect. The actual sites rather than the pooled sites will be specified in data listings.

VP-VLY-686-2102 Protocol

Details of the model and the analyses will be specified in the SAP. All statistical analyses will be performed using SAS®, Version 9.1.3 or higher.

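### Kaplan-Meier curves for discontinuation due to adverse events and due to lack of efficacy ignore competing reasons, so on the ordinary reading they modestly overstate the proportion leaving for each cause

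*SAP*

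**What the plan says.** SAP section 1.2.3 (Subject Disposition) names one method for three endpoints: "Time to discontinuation due to adverse events, lack of efficacy and for any reason will be analyzed using Kaplan-Meier survival techniques". For the arms, "the log-rank test will be used for group comparison". It gives no censoring rule and does not mention competing risks or cumulative incidence.

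The same section also plans crude reporting: "Study completion and reasons for discontinuation for all randomized subjects in the double-blind phase will be summarized for each treatment group", and "Discontinuations by reason will be tabulated by visit for each treatment group". SAP section 1.4.1 (Adverse Events) adds a summary by arm of the proportion of subjects whose AEs led to discontinuation.

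SAP section 1.2 says that these descriptions are general and that full methodology will follow in a separate analysis plan. Unlike several other sections, 1.2.3 does not itself defer its details; it names the method outright.

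**The concern.** Discontinuation for any reason has no competing event within the disposition data, and Kaplan-Meier suits it. The other two endpoints are different. Reasons for leaving are mutually exclusive first events, so leaving for one reason rules out leaving later for another. A Kaplan-Meier curve for one reason that censors the rest treats those who left for other reasons as if they could still have the event. Its complement then estimates a quantity larger than the proportion who actually leave for that cause.

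Two consequences follow. The report would give, for the same event in the same arm, a curve endpoint and a tabulated percentage that disagree without explanation. And because the excess grows with competing dropout, the curves for the two arms can move apart even where the same proportion leaves for that cause in each. Safety and tolerability is a stated secondary objective in the Protocol synopsis, and this is the only time-to-event display of AE discontinuation that the plan names.

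**Working it through.** **Inputs from the documents.** 82 subjects per arm, 164 in total (Protocol, Number of subjects); 8 weeks of double-blind treatment (Protocol, Overall Design); two-sided tests (SAP 1.2.1). There is no planned figure to reproduce, because the documents give no dropout or cause-specific discontinuation rate.

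**Assumptions.** Other reasons are censored; hazards are constant over 8 weeks; the significance level is 0.05 (none is stated); all discontinuation rates below are illustrative.

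**Formulas.** Let p_k be the true week-8 cumulative incidence for cause k, and P the sum over causes.

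- Total cumulative hazard: H = -ln(1 - P)
- Cumulative hazard for cause k: H_k = H × p_k / P
- Kaplan-Meier complement: 1-KM_k = 1 - exp(-H_k)

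**Step 1: one case in full.** AE 10%, lack of efficacy 15%, other 10%, so P = 35%.

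- H = -ln(0.65) = 0.4308
- AE: H_k = 0.4308 × 10/35 = 0.1231; 1-KM = 11.6%
- Lack of efficacy: H_k = 0.4308 × 15/35 = 0.1846; 1-KM = 16.9%
- Other: as for AE, 11.6%

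The three complements sum to 40.0% (from unrounded values) against a true 35%. The any-reason curve gives 1 - exp(-0.4308) = 35%, which is correct.

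**Step 2: the range.**

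| Total dropout | AE: true → 1-KM | Lack of efficacy: true → 1-KM |
|---|---|---|
| 10% | 3.0% → 3.1% | 3.0% → 3.1% |
| 20% | 5.0% → 5.4% | 5.0% → 5.4% |
| 30% | 5.0% → 5.8% | 10.0% → 11.2% |
| 40% | 5.0% → 6.2% | 20.0% → 22.5% |
| 50% | 10.0% → 12.9% | 20.0% → 24.2% |

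**Step 3: equal incidence, unequal competing dropout.** True AE discontinuation is 8% and other reasons 10% in both arms; lack of efficacy is 5% in one arm and 20% in the other.

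- First arm: P = 23%, H = 0.2614, AE H_k = 0.2614 × 8/23 = 0.091; 1-KM = 8.7%
- Second arm: P = 38%, H = 0.4780, AE H_k = 0.4780 × 8/38 = 0.101; 1-KM = 9.6%

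**Step 4: the log-rank test.** Simulated with 82 per arm, 8 weeks and 10,000 runs per setting (Monte Carlo standard error near 5% is √(0.05 × 0.95 / 10,000) = 0.2 points).

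- *Equal AE hazards, unequal competing hazards.* AE cumulative hazard 0.10 in both arms, competing 0.10 versus 0.80: 1-KM is 9.5% in both arms and the test rejects in 4.8% of runs. Here it is the cumulative incidences that differ, 9.1% versus 6.6%. Across all equal-hazard settings, rejection was 4.8% to 5.0%.
- *Equal AE incidence, unequal competing dropout.*

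| AE incidence, both arms | Competing dropout by arm | 1-KM by arm | Rejection |
|---|---|---|---|
| 5% | 10% vs 30% | 5.3% vs 6.0% | 5.0% |
| 10% | 10% vs 30% | 10.6% vs 12.0% | 5.6% |
| 10% | 5% vs 40% | 10.3% vs 12.9% | 8.5% |
| 20% | 5% vs 40% | 20.6% vs 26.3% | 13.9% |

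**The case against.** The strongest reply is that correct cause-specific percentages are already planned. With fixed 8-week follow-up, and if every subject either completes or has a recorded reason for leaving, the crude proportion by reason is the week-8 cumulative incidence in that population. Nothing in the plan says that 1-KM will be reported as the percentage leaving for a cause. This stands, and it limits the consequence. It also means that the curves as planned would disagree with the plan's own tables.

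Second, censoring of other reasons is the ordinary reading and not stated text, and the fuller analysis plan to which SAP section 1.2 defers is not among the documents. That also stands; the point is conditional on that reading.

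Third, the size is small. The gap in Step 3 is 0.9 points, or about 0.7 of a subject among 82. The standard error of a difference between two 8% proportions is √(2 × 0.08 × 0.92 / 82) = 4.2 points. Granted.

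Fourth, cause-specific Kaplan-Meier curves do reconcile with the any-reason curve, by multiplication: 0.884 × 0.831 × 0.884 is about 0.65. That is true, but a reader comparing curves with percentages by reason will expect them to add.

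A reader might go further and infer that the planned group comparison will find arm differences that do not exist. The documents do not support that. The log-rank test with other reasons censored is a valid test of equal cause-specific hazards and held its level in simulation. In Step 3 those hazards really do differ (0.091 versus 0.101), so the separation misleads only someone reading the curves as cumulative incidence.

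**Conclusion.** The point holds as a matter of estimation and display. If other reasons are censored, the curves for AE and lack-of-efficacy discontinuation sit above the proportion leaving for each cause. The direction is certain whenever competing discontinuations come first; the size rests on assumed rates and constant hazards. Up to 40% total dropout it is about a percentage point or less for AEs in most of the range examined, and it reaches several points only at about 50%. Separation of the arms at equal cumulative incidence is real but small unless competing dropout is very unequal, and the documents give no evidence on whether it will be.

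The any-reason analysis and the log-rank test, properly described, are sound. SAP section 1.4 rests the primary safety assessment on event frequencies and not on these curves. The priority is therefore low.

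**What to change.** Amend SAP section 1.2.3 as follows:

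- Keep Kaplan-Meier and the log-rank test for discontinuation for any reason.
- For discontinuation due to AEs and due to lack of efficacy, display Aalen-Johansen cumulative incidence curves by arm, with the other reasons as competing events.
- Keep the log-rank test for these two endpoints, labelled as a comparison of cause-specific hazards with other reasons censored.
- State the population for the curves, so that their week-8 values can be checked against the crude tables.

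Gray's test could be added if a formal comparison of cumulative incidence is wanted; it is not essential.

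The cost is about one sentence in the plan and a standard software option. Reasons for discontinuation are already to be recorded, so no new data are needed. The downside is one more method to describe.

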1.2.4. Demography and Other Baseline Data

Demographic data and subject characteristics at screening/baseline will be listed and summarized by treatment group for all randomized subjects using descriptive statistics.

Past and current medical history will be summarized by treatment group using the system organ class (SOC) as coded using the Medical Dictionary for Regulatory Activities (MedDRA) coding dictionary.

Past medical conditions will be defined as an onset date prior to randomization (Visit 2) and resolved (not on-going) as of Visit 2. Current medical conditions, defined as an onset date on or after the date of randomization (Visit 2) or an onset date prior to randomization (Visit 2) and unresolved (on-going) as of Visit 2, will be reported separately, but similarly to the past medical

conditions. If both a past and a current (on-going) medical condition record are indicated for a condition, the condition will be presented under current medical conditions only.

1.2.5. Study Medication

The number of subjects at each visit will be summarized by treatment group.

The compliance to study medication, as recorded in the CRF, will also be summarized by treatment group. The proportion of subjects who are significantly noncompliant in the double-blind phase, as noted in Section 7.3 of this protocol, will be summarized by treatment groups.

1.2.6. Prior/Concomitant Therapy

Any medications or therapy present before the first dose of study medication (Visit 2) will be considered as prior medications. Concomitant medications (medications present while on study medication) will be recorded throughout the study and at early discontinuation. These medications will be coded using the WHO-drug dictionary. The number of subjects from the Safety Population using prior or concomitant medications will be categorized by the WHO-drug category and preferred term, and presented for each treatment group. In any given category (e.g., drug category) a subject will be counted only once.

1.3. Efficacy Data Analysis

1.3.1. Primary Outcome and Methodology

The primary efficacy outcome measure for the double-blind phase will be the mean change from baseline in pruritus symptoms. A detailed description of the primary analysis model will be included in the SAP.

As stated previously, any changes in the statistical methods that occur prior to database lock will be documented in the SAP and will not require a protocol amendment.

1.3.2. Secondary Efficacy Analysis

The secondary efficacy outcomes include:

- DDSS
- Itch questionnaires including VAS, VRS, DDIS
- SCORAD index;

- Objective SCORAD;
- EASI:
- PGI-C;
- CGI-C;
- PBI;
- Skindex-16;
- Pharmacokinetic-Pharmacodynamic correlation.

Continuous endpoints will be summarized and analyzed in a manner similar to the primary endpoint. Details of the analysis will be described in the SAP.

Categorical variables will be evaluated as described in the SAP. Time to event data will be analyzed using the Kaplan-Meier method, and the treatment group differences will be tested by the log-rank test. Details of the analysis will be described in the SAP.

1.4. Safety Data Analysis

The primary assessment of safety will be based on the frequency of treatment-emergent adverse events (TEAEs), serious adverse events (SAEs) and on the frequency of clinically notable abnormal vital signs, electrocardiograms (ECGs) and laboratory values. Other safety evaluations include changes in vital signs, changes in clinical laboratory evaluations, and changes in ECGs, physical exam findings during treatment, and suicide ideation and behavior events.

1.4.1. Adverse Events

Adverse events will be recorded throughout the study and at early discontinuation. Adverse events and medical conditions will be coded using the Medical Dictionary for Regulatory Activities (MedDRA) coding dictionary. Treatment-emergent adverse events will be defined as those events, which are newly occurring or worsening from baseline. In all cases only treatment emergent adverse events will be summarized.

Treatment-emergent adverse events will be summarized within each treatment group by primary system organ class and preferred term. (*NOTE*: In any given category [e.g. body system] a subject will only be counted once.) The incidence rates of TEAEs will be analyzed as described in the SAP. Similar displays will be provided for SAE and prior (conditions ending prior to the first dose of study medication and current (conditions present while on study medication) medical conditions.

Adverse events will further be categorized by severity, relationship to study medication, and action taken. Other information collected will be listed, as appropriate. Any event starting more than 3 days after the final dose of study medication will be excluded from the above tables and only listed, unless the event caused discontinuation.

The proportions of subjects experiencing SAEs and AEs resulting in discontinuation from the study will be summarized by treatment groups.

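### The 3-day cut-off in SAP 1.4.1 leaves late SAEs that did not cause discontinuation out of the by-arm SAE table, and the SAE proportions carry no matching rule

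*SAP*

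**What the plan says.** All of the relevant adverse event text is in SAP 1.4.1, and its order matters.

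1. Treatment emergence is defined without an end date: "Treatment-emergent adverse events will be defined as those events, which are newly occurring or worsening from baseline".
2. Summaries are restricted to such events: "In all cases only treatment emergent adverse events will be summarized".
3. Treatment-emergent events are tabulated within each arm by system organ class (SOC) and preferred term, and the same form is planned for serious events: "Similar displays will be provided for SAE".
4. The cut-off follows: "Any event starting more than 3 days after the final dose of study medication will be excluded from the above tables and only listed". Its only exception is "unless the event caused discontinuation".
5. A separate paragraph after the cut-off adds: "The proportions of subjects experiencing SAEs and AEs resulting in discontinuation from the study will be summarized by treatment groups". It gives no time limit.

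On collection, the same section says: "Adverse events will be recorded throughout the study and at early discontinuation". SAP 1.4 makes SAE frequency one of the components of the primary safety assessment.

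**The concern.** The cut-off applies to any event, whether or not it is serious. A cut-off for routine adverse events keeps the tables focused on the period of exposure. Applied to SAEs, it moves a recorded serious event out of a by-arm display of a primary safety measure and into a listing, where the arms are not compared.

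The SAE proportions come after the rule and carry no cut-off of their own. The plan therefore describes two by-arm SAE outputs without saying that they share one counting rule. A reader of the report could find two different SAE counts for the same arm, or could find a late SAE in neither output.

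**Working it through.** The documents give no SAE rate and no expected number of late events, so there is no planned figure to reproduce. The check is of wording and sequence, followed by one illustration of size.

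**Step 1: is the SAE table covered by the cut-off?** The SOC and preferred term display for SAEs is described before the cut-off, and the cut-off applies to the tables above it without further restriction. The SAE table is therefore covered.

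**Step 2: is a late SAE exempt?** Only if it caused discontinuation. Neither seriousness nor a fatal outcome is named as an exception.

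**Step 3: does the definition of treatment emergence settle the matter?** No. It has no end date, so an SAE that is new or worse after baseline qualifies however late it begins. The restriction to treatment-emergent events does not remove it from any summary. Only the 3-day sentence does.

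**Step 4: what happens in the SAE proportions?** Take a late SAE that did not cause discontinuation.

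| Reading of the proportions sentence | SAE table | SAE proportions | Result |
|---|---|---|---|
| All SAEs, plus other events leading to discontinuation; no cut-off (natural reading) | not counted | counted | the two outputs disagree |
| All SAEs, with the 3-day rule carried over | not counted | not counted | outputs agree; event in no by-arm SAE summary |
| Only SAEs that led to discontinuation | not counted | not counted | no mismatch from this rule; event in no by-arm SAE summary |

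**Step 5: size, for illustration.** Inputs: 82 subjects per arm (Protocol Synopsis, Number of subjects) and a safety population of randomised subjects who received a dose (SAP 1.2.2). Assumption: all 82 are dosed.

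- Change in an arm's SAE table per subject whose only SAE is late and not exempt: 1/82 = 1.2 percentage points.
- Assumed range of 0 to 3 such subjects in an arm: 0/82 = 0 to 3/82 = 3.7 percentage points.
- Example: an arm has 2 subjects with SAEs, one of them late. On the first reading, the table shows 1/82 = 1.2% and the proportion shows 2/82 = 2.4%. On the second reading, both show 1/82 = 1.2%.

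**Step 6: who can be affected?** The schedule in Protocol Table 1 ends at V6 (Day 56 or early termination) and shows no later visit. Late events should arise mainly in subjects who stop drug more than 3 days before their last contact. The text supplied does not say how long SAEs are collected after the last dose, so the number cannot be estimated.

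**The case against.** The strongest reply is that little is at stake. No recorded event is lost, because late events stay in the listings. The affected set is narrow, and no efficacy result or test depends on it. All of this stands, and it limits the weight of the point.

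The discontinuation exception also matters. A reader might infer that late SAEs and deaths are excluded without relief. The documents do not support that: in the proportions sentence, discontinuation means leaving the study. If the exception has the same meaning, a late SAE or death recorded as ending participation stays in the table. Even so, inclusion then depends on how the reason for leaving is coded, not on seriousness. Non-terminating SAEs, and events after a subject has already left, remain uncovered.

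A reader might also infer that the two SAE outputs must conflict. That depends on the proportions sentence, which can be read as covering only events that led to discontinuation. That is the less natural reading. It removes the mismatch but leaves the omission.

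It may be said that SAP 1.2 describes the analyses in general terms and leaves the complete methodology to a later SAP. For adverse events, however, section 1.4.1 defers only the analysis of incidence rates. The 3-day rule is stated outright and would be followed as written unless changed.

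Finally, a reader might infer from Protocol Table 1, footnote 11, that completers cannot be affected because V6 falls shortly after a dose. That footnote times the pruritus assessment, not the last contact or the end of SAE reporting.

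**Conclusion.** The point holds as a defect in a stated rule. Followed as written, a recorded SAE that begins over 3 days after the last dose and did not cause discontinuation is left out of the by-arm SAE table. Depending on how the next paragraph is read, that event either makes the two SAE outputs disagree or is missing from every by-arm SAE summary. No available reading removes both problems.

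The reach is probably small, and the number of subjects affected is unknown. The figure of 1.2 points per subject is an illustration that assumes 82 dosed subjects in the arm; it is not a forecast. The documents do not support a claim that serious events are lost or that the trial's safety conclusion would change. The reason to act is that SAE frequency is a primary safety measure, one subject visibly changes an arm's count at this sample size, and the correction is simple.

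**What to change.** In SAP 1.4.1:

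- Limit the 3-day exclusion, together with its exception for events that caused discontinuation, to non-serious events.
- State that all recorded SAEs that start or worsen after the first dose, and all deaths after the first dose, are tabulated by arm under the same rule in both the SAE table and the SAE proportions.

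Stating one common finite window for both outputs would remove the mismatch, but later SAEs would still be left out of the by-arm summaries.

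The cost is wording only: no new visits, data or tables. SAP 1.2 allows changes of method before database lock to be documented in the SAP without amending the protocol. The downside is that SAE counts may be slightly higher and may include some events unrelated to the drug.
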